5.4. Derived and Computed Variables

Table 3 provides the rules for derived and computed variables which have been initially identified as important for the analysis of the safety or efficacy as appropriate. It is expected that additional variables will be required. The SAP will not be amended for additional variables that are not related to the primary target or key secondary target variables. Any additional derived or computed variables will be identified and documented in the SAS programs that create the analysis files.

The birth date for each subject is collected on the eCRF. To be consistent with all the other TransCon hGH studies, the 15th day of the reported month is used to calculate the age and related scores. In such case, all the height SDS for the subjects will be calculated using 15th as the birth day. The HSDS reported in the eCRF will not be used as it is based on the actual birth date reported by the subject. FMD K&L will utilize the published SAS macro to calculate the height SDS and no independent QC is required for published SAS macro.

Table 3. Parameter Definition

Parameter	Definition
Annualized Height Velocity at visit x (HV) cm/year	$((\text{Height (Visit } x) - \text{Height (Visit } 1)) * 365) / (\text{Date (Visit } x) - \text{Date (Visit } 1))$ 
From the 15-month (65 weeks) visit onwards, the baseline value used for each successive HV calculation was the patient's height at the visit 52 weeks previously, e.g. height at 13 week served as the baseline value to determine HV at the 65 week ('moving 52 weeks HV basis'). If height at visit 52 weeks previously is missing then most recent height prior to the visit will be used.

Height Deviation Standardized Score (HSDS)	Height SDS will be derived using CDC 2000 (United States of America). A standard SAS program is published at: https://www.cdc.gov/nccdphp/dnpao/growthcharts/resources/sas.htm
Change from baseline	The value of each variable at each post-baseline time point minus the baseline score.
Normalized serum IGF-1 SDS	Proportion of subjects with IGF-1 Standard Deviation Score (SDS) of 0 to +2.0. Also derive for -2.0 to +2.0, -1.0 to +2.0.
Parents' Height SDS	$((\text{Parents Height}/M)^L - 1) / (L \times S)$ 
Where M=median, S= generalized coefficient of variation, and L= power in the Box-Cox transformation, the M, S, L values are obtained from the CDC website; Percentile Data Files with LMS Values

Total Duration of Treatment (day)	Last treatment date of the extension study – first treatment date of the extension study +7
Total Duration of Treatment (week)	Round (Total Duration of Treatment in days /7) to the nearest integer

Treatment Compliance	Total number of dose taken in the extension study/Total duration of treatment (week) in the extension study
----------------------	---

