8.2. PREMATURE SUBJECT WITHDRAWAL

Early withdrawal occurs when an enrolled subject ceases participation in the trial, regardless of the circumstances, prior to the expected completion of the trial, which in this study is until a) the product is approved and commercially available, b) the Sponsor makes alternative arrangements for continued subject access to hGH treatment, or c) treatment for pediatric growth hormone deficiency is no longer considered appropriate. Additionally, the investigator may discontinue the treatment of a subject at any time if considered to be in the subject's best interest. If treatment is permanently discontinued for any reason, trial participation should be discontinued. If the subject completes the trial or discontinues prematurely, a Completion Visit/Early Termination Visit should be performed. See Section 7.3.1 for a list of valid reasons for early termination of subjects from the trial.

For trial discontinuations, the investigator should schedule a Completion Visit/Early Termination Visit to collect data, particularly AE data reported up to 14 days after the final dose of TransCon hGH (if applicable), and to collect blood for laboratory evaluations. This visit should contain all assessments from Visit 5 (Week 52, see Schedule of Events, Section 18.2), as applicable, and will be documented in the eCRF together with the reason(s) for trial discontinuation.

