- When the GH Auto-Injector is available, thorough onsite training of investigational product preparation and administration will occur at the earliest regularly scheduled visit (including the 1st visit upon transition of the GH Auto-Injector in the US where the GH Auto-Injector will be used.
- Includes instructions that administration of investigational product should occur at approximately the same time of day on the same day of the week throughout the trial. Details regarding adjustment of a subject's established dose day/time are provided in the trial manual.

9. Subject diary completion review, as needed

- May also be performed at other visits, as needed
- Includes reminder to complete Week 6 PRO questionnaires prior to 6th dose of investigational product
- In those subjects using the GH Auto-Injector: includes reminder to complete the Device Usability Questionnaire (DUQ) on the day of 6th dose using the GH Auto-Injector

10. Patient-reported outcome questionnaires

- Convenience and Overall Satisfaction domains (C&OS) of the Treatment and Satisfaction Questionnaire for Medication (TSQM-9)
 - For the parent (C&OS-P)
- Child Sheehan Disability Scale
 - For the parent (CSDS-P)
 - **For the child ≥ 9 years old only:** (CSDS-C)

11. Investigational product dose adjustment (from prior trial), as needed

- Investigational product volume is based on weight measurement obtained at Visit 1 and the Bracketed Weight Table for TransCon hGH, or the GH Auto-Injector dosing table

12. Investigational product and subject diary dispensing

In the unusual event there is a gap of 4 to approximately 6 weeks between the assessments done for Visit 1 and Day 1 (first dose), then all of the above should be repeated except physical exam, blood collection, and bone age x-ray.

Following Visit 1, TransCon hGH will be administered by subject/parent/legal guardian/caregiver as a once weekly SC injection. Once weekly healthcare services may be offered for the first 4 weeks of a new treatment (eg, subjects beginning TransCon hGH in this trial) to accommodate home administration of TransCon hGH. Extended support may be offered until subjects/parents/legal guardians/caregivers are comfortable assuming responsibility for

administration of the investigational product. See Section 9.3 for details regarding TransCon hGH administration and Section 9.6 for details regarding dose adjustments.

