8.6. Exposure and Compliance

Summary tables for extension study will be presented for the following variables:

- Total duration of treatment
- Total number of actual doses

- Total actual dosage (mg)
- Compliance rate

The dosage (mg) is the product of the dose volume (mL) and dose concentration (mg/mL) reported in the eCRF. When there are three or more consecutive doses with more than 15% difference between actual dose and expected dose (0.24mg/kg/week), it will be considered as a dose reduction/increase. The frequency and percentages of subjects for dose not changed, dose increased or decreased will also be summarized by visit and overall.

The compliance rate will be calculated based on the rules in Section 5.4. Compliance rate will be summarized using the following categorization; <80%, ≥80%, ≥90%, ≥95% and 100%.

Listings will be presented for all exposure information.

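### The compliance denominator ends at the last dose taken, so weekly doses still due but missed after that dose are not counted

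*SAP*

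**What the plan says.** SAP Section 5.4, Table 3, builds compliance in three steps:

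- Duration in days: "Last treatment date of the extension study – first treatment date of the extension study +7".
- Duration in weeks: "Round (Total Duration of Treatment in days /7) to the nearest integer".
- Compliance: "Total number of dose taken in the extension study/Total duration of treatment (week) in the extension study".

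SAP Section 8.6 gives no other denominator: "The compliance rate will be calculated based on the rules in Section 5.4". It reports the result in categories from below 80% up to 100%.

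The protocol sets the dosing frequency: "TransCon hGH will be administered by subject/parent/legal guardian/caregiver as a once weekly SC injection" (Section 10.2). Section 9.8 bases compliance on drug accountability and the subject diary and names no denominator. Sections 10.2.2.2 and 10.2.2.3 and the Schedule of Events (Section 18.2) call for a compliance review from diary and returned product at each scheduled visit after Visit 1. On leaving the trial, Section 8.2 says: "If treatment is permanently discontinued for any reason, trial participation should be discontinued".

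**The concern.** The added 7 days credit one dosing interval after the final injection. The last treatment date is therefore naturally read as the date of the last dose taken, and not as the final visit or a data cut-off. On that reading, a dose that was due and missed after the last dose taken leaves the numerator and the denominator together. Identical non-adherence is scored differently according to when it happens: a gap in mid-course lowers compliance, while the same gap at the end of the record has no effect. The error runs in one direction only, because a terminal gap cannot lower the reported figure.

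At stake is how the exposure and compliance tables are read. Protocol Sections 5.1 and 5.5 give better compliance as a reason for weekly dosing, and Section 14.2 says the trial is meant to support market approval. A table that shows a child who had drifted off treatment as fully compliant would mislead on that subject.

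**Working it through.** The plan states no compliance figure to reproduce, so the formula is applied directly.

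**Inputs.** One dose per week (Protocol Section 10.2); the SAP Table 3 formula; visits 13 weeks apart, ±2 weeks (Protocol Section 10.2). The numbers of missed doses and the follow-up lengths below are assumptions.

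**Formulas.** With weekly doses from Day 1:

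- SAP compliance = doses taken / round((last dose day − first dose day + 7)/7).
- Comparison = doses taken / weekly doses due to the end of observation.

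**Check with perfect adherence.** 52 weekly doses put the last dose on Day 1 + 7×51 = 358. Duration is 358 − 1 + 7 = 364 days, or 52 weeks, and 52/52 = 100%. The formula works when nothing is missed.

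**Twelve doses missed at the end of 52 weeks.** The 40th dose falls on Day 1 + 7×39 = 274. Duration is 274 − 1 + 7 = 280 days, or 40 weeks.

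- SAP: 40/40 = 100%.
- Doses due: 40/52 = 76.9%.

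**The same twelve missed in mid-course.** The last dose is on Day 358, so duration is again 52 weeks and the SAP gives 40/52 = 76.9%. Mid-course misses are counted correctly.

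**Other terminal gaps over 52 weeks.** The SAP gives 100% in every row.

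| Final doses missed | Doses taken / doses due |
|---|---|
| 2 | 50/52 = 96.2% |
| 4 | 48/52 = 92.3% |
| 8 | 44/52 = 84.6% |
| 11 | 41/52 = 78.8% |
| 13 | 39/52 = 75.0% |

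**Both kinds of miss.** With 3 missed in mid-course and 6 at the end, the SAP gives 43/46 = 93.5% against 43/52 = 82.7%.

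**Effect of follow-up length.** If only the final k doses of T weeks are missed, the overstatement is k/T. For k = 4 it is 30.8 points at 13 weeks, 15.4 at 26, 7.7 at 52 and 3.8 at 104.

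**Cohort mean.** If a share s of subjects each miss k final doses over 52 weeks, the mean is overstated by s×k/52. With s from 5% to 20% and k from 2 to 8 (assumed), this runs from 0.05×2/52 = 0.2 points to 0.20×8/52 = 3.1 points.

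**The case against.** The case for the SAP rule has real substance.

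- A reader might infer that no dose missed before withdrawal or cut-off is ever counted. The formula does not support that: every miss between the first and last dose is counted, so intermittent non-adherence is captured.
- A reader might infer that, because stopping treatment ends participation, a long gap before the termination visit is mostly missed dosing. The documents do not show this. After a documented stop no dose is due, and Protocol Sections 8.2 and 9.6.2 describe stops that are not non-adherence, such as closed epiphyses, pregnancy or the investigator's judgement of the child's interest.
- A reader might conclude that the denominator should simply run to the data cut-off, since SAP Section 4.1 allows interim analyses. That would do harm. Diaries and used product come back only at visits (Protocol Sections 9.8 and 11.8). A fully adherent child last seen at Week 40, with a cut at Week 52, would score 40/52 = 77% because 12 doses had not yet been reported. Ending at the last recorded dose avoids that error.
- Adherence up to the last dose is a recognisable on-treatment measure. Withdrawals and their reasons (SAP Section 6.1), treatment duration and number of doses (SAP Section 8.6) are reported separately.
- Scheduled visits fall 5 days (±1) after a dose, so a dosing child seen on time has no uncounted gap.

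All of this stands and narrows the point. It leaves one case unanswered: a child who stops injecting without a documented decision and is then seen at a later visit, where diary and returned product show the missed doses. Those doses were due, the trial knows they were missed, and the formula drops them.

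**Conclusion.** The point holds in a limited form. For a subject with doses still due and missed after the last dose taken, and no documented decision to stop, SAP compliance is overstated. The per-subject error can be large: 100% instead of 77% in the 40-dose example, a shift that fits within one visit interval. It shrinks as follow-up lengthens. At cohort level the size is unknown, because the documents give no frequency for such gaps. It is probably small, at 0.2 to 3.1 points under the assumed ranges.

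The conclusion rests on reading the last treatment date as the last dose taken, and on a weekly schedule. Compliance is not an endpoint in Protocol Section 14.1 or SAP Section 3.3, so no efficacy or safety endpoint changes. This is a worthwhile clarification and not a threat to the trial's conclusions.

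**What to change.** Keep first-to-last dose plus 7 days as the exposure duration. For compliance, replace the denominator with the number of weekly doses due from the first extension dose to the earlier of:

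- (a) the documented treatment stop or completion; and
- (b) the last visit, including the Completion or Early Termination Visit, at which diary and returned product were reviewed.

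Further rules:

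- Count only doses taken up to the same date.
- At an interim cut, use the last such visit on or before the cut. The adherent child reviewed at Week 40 then scores 40/40 = 100%.
- Exclude documented interruptions directed by the investigator or the protocol.
- For subjects lost to follow-up, use the last such visit and report the later loss under disposition.

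The cost is a change to SAP wording and one derived variable, drawn on reviews the protocol already requires. Reported compliance will fall slightly, and doses after the last reviewed visit will not be assessed. One item needs confirming: Protocol Section 8.2 has the termination visit and the reason for discontinuation entered in the eCRF, but the documents do not show that the date of a decision to stop treatment is captured.

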5.5. Analysis Population

The Full Analysis Set includes all subjects who signed inform consent for this study and received at least one dose of study drug during the trial. The efficacy and safety analysis will be performed based on full analysis set.

6. Subject Disposition

6.1. Disposition

The number of subjects who are enrolled for the trial, i.e., the subjects who signed inform consent, the number of subjects who received any doses and the number of subjects who complete the trial will be presented. The frequency and percentage of subjects who withdraw or discontinue from the trial, and the reason for withdrawal or discontinuation, will also be summarized.

The summaries will be presented in a table and subject disposition data will be presented in a listing.

6.2. Protocol Deviations

A list of major protocol deviations that could significantly affect study assessments will be identified by Clinical and the Medical Experts based on the pre-specified criteria. A data review meeting will be held to determine this list. This list will be finalized prior to database lock. A listing will be produced for protocol deviation.

7. Demographics and Other Characteristics

7.1. Demographics and Disease Characteristics

Descriptive summaries of the parent study baseline and extension study baseline will be summarized for the full analysis set.

- Extension Study Baseline Demographics and Disease Characteristics:
 - o Age (years) at Visit 1
 - o Age category (<3 years, ≥3 to <6 years, [≥6 to <11 years for girls, ≥ 6 to <12 years for boys] and [≥11 years for girls, ≥12 years for boys])
 - o Gender
 - o Race
 - o Ethnicity
 - o Region (North America, Europe, and Oceania)
 - o Absolute height (cm)
 - o Height SDS
 - o Weight (kg)
 - o Body mass index (BMI) (kg/m²)
 - o Pubertal status (Tanner stage)
 - o Mother's height (cm)
 - o Father's height (cm)
 - o Average-parental height SDS
 - o IGF-1
 - o IGF-1 SDS
 - o IGFBP-3
 - o Prior use of hGH therapy (Daily GH or TransCon, Dose and duration)
 - o Bone Age
 - o Peak stimulated GH (levels ≤5 ng/mL, >5 ng/mL) at diagnosis

7.2. Medical History

Medical history will be coded with Medical Dictionary for Regulatory Activities (MedDRA) (Version 19.0 or later). Incidences of findings in medical history will be summarized by system organ class (SOC) and preferred term.

7.3. Prior and Concomitant Medications

All medications will be coded using the World Health Organization (WHO) Drug Dictionary (Version March 2018 or later). The frequency and percentage of all prior and concomitant medications will be summarized by Anatomical Therapeutic Chemical (ATC) classification and preferred term. Listings of all medications will also be provided.

7.3.1. Prior Medication

Prior medication is defined as any medication started before the date of the first dose of investigational product in this extension study, where the medication start date is prior to the date of the first dose date in this extension study.

If the start/stop dates of a medication are partially or completely missing, then the medication will be assumed to be a prior medication if it cannot be definitely shown that it started on or after the first dose of the investigational product. Missing dates will not be replaced.

7.3.2. Concomitant Medication

Concomitant medication is defined as medication taken on or after the date of the first dose of investigational product in this extension study, where the medication end date is on or after first dose date in this extension study (or ongoing)]

If the start/stop dates of a medication are partially or completely missing, then the medication will be assumed to be concomitant if it cannot be definitely shown that it was not administered during the treatment period. Missing dates will not be replaced.

Permitted Concomitant Medications

- Replacement therapy for other non-GH pituitary deficiencies. As hGH may enhance the transformation of hydrocortisone to cortisone, the investigator may increase the dose of hydrocortisone replacement therapy if needed (eg, for anticipated stress).
- Treatment for diabetes
- Over-the-counter vitamins, minerals, or other dietary supplements only if their use is agreed to by the investigator.

Prohibited Concomitant Medications

- Weight-reducing drugs or appetite suppressants, unless used for management of ADHD
- hGH therapies other than TransCon hGH

Use of prohibited concomitant medications will be summarized and listed.

8. Safety Analysis

The safety endpoints (Section 3.3.1) are measured throughout the long term TransCon hGH treatment. These safety variables will be summarized in tables and all safety evaluations will also be listed.

8.1. Adverse Events

AE is defined as any untoward medical occurrence in a clinical investigation subject administered a pharmaceutical product and which does not necessarily have a causal relationship with the treatment. An AE can therefore be any unfavorable and unintended sign (including

abnormal laboratory finding), symptom, or disease temporally associated with the use of a medicinal (investigational) product, whether or not related to that product. An AE can arise with any use (e.g., in combination with another drug), route of administration, formulation, or dose, including an overdose.

An AE is considered treatment emergent, i.e., Treatment Emergent Adverse Event (TEAE), is any AE that was first occurred or worsened after the first dose in this extension study and before the end of study. If the AE has any missing start date, the rules stated in Section 5.2 will be applied to determine if it is treatment-emergent.

A serious AE (SAE) is SAE is any untoward medical occurrence that:

- Results in death
- Is life-threatening
- Requires inpatient hospitalization or prolongation of an existing hospitalization
- Results in persistent or significant disability/incapacity
- Is a congenital anomaly/birth defect

Summaries of incidence rates (frequencies and percentages) of individual TEAEs by MedDRA SOC and preferred term will be prepared. Such summaries will be displayed for all TEAEs, TEAEs by maximum intensity, and TEAEs by strongest relationship to study drug. In addition, related TEAE, non-related TEAE, TEAE leading to study drug discontinuation, and serious TEAE, by SOC, the preferred term and TEAE by preferred term will be also summarized. Especially, related includes definite, probable and possible relationship. Not-related includes unlikely/remote and unrelated/not related.

Each subject will be counted only once within each preferred term. If a subject experience more than one TEAE within a preferred term, only the TEAE with the strongest relationship or the maximum intensity, as appropriate, will be included in the summaries of relationship and intensity.

Data listing of AEs, TEAE leading to study drug discontinuation, serious TEAE will also be provided.

